8.6 Pharmacokinetic Data Handling

8.6.1 Pharmacokinetic Plasma Drug Concentration Data

Pharmacokinetic concentration values below the quantification limit (BLQ) will be treated as zero for the calculation of summary statistics.

Individual values that are BLQ will be presented as “BLQ” in the concentration data listing.

No imputation will be performed for missing concentration.

8.7 Handling of Partial Dates for AEs

When determining the treatment emergent AE, partial dates will be handled as follows.

- If the day of the month is missing, the onset day will be set to the first day of the month unless it is the same month and year as first dose date. In this case, the onset date will be assumed to be the first date of treatment.
- If the onset day and month are both missing, the day and month will be assumed to be January 1, unless the event occurred in the same year as the study treatment. In this case, the event onset will be coded to the day of treatment to conservatively report the event as treatment-emergent.
- A missing onset date will be coded as the day of treatment. If the resulting onset date is after a reported date of resolution, the onset date will be set equal to the date of resolution.
- Imputation of partial dates is used only to determine whether an event is treatment-emergent; data listings will present the partial date as recorded in the eCRF.

8.8 Handling of Partial Dates for Medications

A medication with a completely missing start date will be considered a prior medication. A medication with a completely missing stop date will be considered to be ongoing.

When determining prior or concomitant medications, partial start dates of prior and concomitant medications will be assumed to be the earliest possible date consistent with the partial date. Partial stop dates of prior and concomitant medications will be assumed to be the latest possible date consistent with the partial date.

9 Changes to the Planned Analyses in the Protocol(s)

Because protocol amendment dated 02 February 2018 removed randomization portion during the trial, there will not be enough samples size to do the following analysis specified in the original protocol dated dated 27 July 2017. Therefore, the following analysis will not be performed for CSR.

- A secondary analysis will compare the proportions of subjects who are deemed a success at the end of the randomized fixed-dose period between those randomized to the ENT-01 arm and those randomized to the placebo arm. Subjects to be included in this analysis will only be those who have been randomized. If the number of subjects for this analysis is between 20 and 30, a Fisher's exact test will be used to compare the proportions of subjects who are deemed a success at the end of randomization period between the two randomized arms.

The protocol also proposed the following analysis as below:

- Another secondary analysis will compare the proportions of subjects who are a success (compared to baseline) between the end of the first week of the washout period (period 5) and the end of the fixed-dose period (period 4). This analysis will consist only of those subjects with assessments at baseline (end of run-in period, Period 3.1), the end of Period 4, and the end of Period 5. If the number of subjects for this analysis is between 17 and 20 subjects, this analysis will be done using an exact sign test of equality of paired proportions.

In this analysis, using the end of the first week of washout is not consistent with the time frame for other PD parameters (note: other PD parameters' are all evaluated using two weeks of washout data, i.e., the end of 2 weeks). Therefore, it was determined we would not do this analysis for CSR.

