Patients will be taken off study drug. They will continue to keep a daily diary throughout the period. They will be contacted by phone daily during Week One to check diaries and laxative use. During the first week of the wash-out period they will only use rescue medication as needed. During the second week, they will be restarted on all original medications including laxatives but will continue their diaries until the termination of the study. They will continue to wear the I-Button for the first 5 days of this period. During the last visit, the UPDRS, BDI, Trail-Making A and B, MMSE, PFS-16, NMSQ, UM-PDHQ, RBDQ, PDSS, PAC-SYM and PAC-QOL will be administered

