APPENDIX 2: SCHEDULES OF EVENTS

STAGE 1

Period	Ru Ser	1 n-In ntinel wks	2.1 Single Dose 3-8 wks	2.2 Wash-Out 2 wks
	D1	D14	D1	
Consent	X			
Demographics	X			
Inclusion/exclusion	X	x		
Medical history	X			
Physical exam	X		X	x
Vital signs ¹	X		X	x
Rome-IV	X			
Blood chemistry	X		х	х
Hematology	X			
Urinalysis	X			х
Fecal occult blood	X		х	х
EKG	X		х	х
Pregnancy test	X			
Monitoring			х	х
Discontinue medications	X			
Re-start medications				х
Diary entries	X	x	х	х
UPDRS	X		X^4	x ²
I-Button ³	X	х	X	
PAC-QOL	X	х	X ⁴	x ²
PAC_SYM	X	X	X ⁴	x ²
RBDQ	X		X ⁴	x ²
NMSQ	х		X ⁴	x ²
PFS-16	х		X ⁴	x ²
UM-PDHQ	х		X ⁴	x ²

BDI	X		X ⁴	\mathbf{x}^2
Trail-making A and B	X		X ⁴	x ²
MMSE	X		X ⁴	\mathbf{x}^2
Adverse events		Х	X	х
PK samples			X ⁵	
Schedule visit days	X			
Administer ENT Dose			X	
Record Medications	X	Х	X	x
Daily phone calls to on non-visit days		Х	X	х

¹Vital signs taken before dose and 2 hours after dose

²End of period 2

³I-Button placed days 9 of run-in periods and worn continuously through day 5 of wash-out periods.

⁴Surveys taken at last dosing visit

⁵PK samples taken pre-dose and 1, 2, 4, 8 and 24 hours post-dose

STAGE 2

		Period 3.1 Run-In					Period 3.2 Multiple Dose		Period 4 domized Treat	ment	Period 5 Wash-Out	
	Day 1 Visit 1	Days 2-7, 9- 10, 12-13 Calls	Day 8 Call	Day 11 Visit 2	Day 14 Call	Days 1-13, 15-16 Calls	Day 14 Call	Day 1 Visit 3 ⁶	Days 2-5 Calls	Day 6 Visit 4	Days 1-7 Calls	Day 14 Visit 5
Informed Consent	X											
Inclusion/Exclusion Criteria	X											
Demographics/Medical History	X											
Prior and Con Meds	X											
Complete Physical Exam	X											X
Height	X											
Weight	X			X				X		X		X
Vital Signs ¹	X			X				X		X		X
ECG	X							X				X
Local Labs - Chemistry, Hematology	X							X		X		X
Local Labs - Urinalysis, Serum Pregnancy	X											
Fecal Occult Blood	X							X				X
Randomization								X				
Study Drug Dispense, Accountability, or Collection				Х				X		X		
Reminder to Begin Taking Study Drug the Next Morning					X							
Instructions to Discontinue Laxatives and other BM Medications	X											
Instructions to Resume Laxatives and other BM medications												X
Stool and Sleep eDiary Instruction/Review	X	X	X	X	X	X	X	X	X	X	X	X
AE Review		X	X	X	X	X	X	X	X	X	X	X
Rome IV questionnaire	X		X									
UPDRS	X							X				X
PAC-QOL and PAC-SYM	X				X		X	X		X		X
Questionnaires - BDI, NMSQ, PFS-16, UM- PDHQ, MMSE, Trail-Making A and B, RBDQ and PDSS	X							X		X		Х

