Informed Consent	X											
Inclusion/Exclusion Criteria	X											
Demographics/Medical History	X											
Prior and Con Meds	X											
Complete Physical Exam	X											X
Height	X											
Weight	X			X				X		X		X
Vital Signs ¹	X			X				X		X		X
ECG	X							X				X
Local Labs -Chemistry, Hematology	X							X		X		X
Local Labs - Urinalysis, Serum Pregnancy	X											
Fecal Occult Blood	X							X				X
Randomization								X				
Study Drug Dispense, Accountability, or Collection				X				X		X		
Reminder to Begin Taking Study Drug the Next Morning					X							
Instructions to Discontinue Laxatives and other BM Medication	X											
Instructions to Discontinue Laxatives and other BM medications												X
Stool and Sleep eDiary Instruction/Review	X	X	X	X	X	X	X	X	X	X	X	X
AE Review		X	X	X	X	X	X	X	X	X	X	X
Rome IV questionnaire	X		X									
UPDRS	X							X				X
PAC-QOL and PAC-SYM	X				X		X	X		X		X
Questionnaires- BDI, NMSQ, PFS-16, UM- PDHQ, MMSE, Trail-Making A and B, RBDQ and PDSS	X							X		X		X
Sitzmarks Capsule Distributions ²	X							X				
Reminder to Take Sitzmarks Capsules ³		X							X			
Abdominal X-Ray				X						X		
Dispense I-Button ⁴	X											

Scheduled Assessments	Period 3.1 Run-In					Period 3.2 Multiple Dose		Period 4 Randomized Treatment			Period 5 Wash-Out	
	Day 1 Visit 1	Days 2-7, 9- 10, 12-13 Calls	Day 8 Call	Day 11 Visit 2	Day 14 Call	Days. 1-13, 15-16 Calls	Day 14 Call	Day 1 Visit 3 ⁶	Days 2-5 Calls	Day 6 Visit 4	Days 1-7 Calls	Day 14 Visit 5
PK Draws & LFT ⁵								X		X		
Phone Call		X	X		X	X	X		X		X	

¹ For PK patients, vital signs taken pre-dose and 2 hours after dose. Blood pressure will be taken for all patients twice, first lying down and then after 5 minutes of sitting or standing from the recumbent position. All other vital signs will be measured after the patient has been resting in a sitting position for at least 5 minutes.

²Sitzmark capsules are dispensed to patients at Visit 1 with instructions to take one a day on Days 8, 9, and 10 of the Run-In period for the abdominal X-ray on Day 11. Patients will receive more Sitzmark capsules at Visit 3 with instructions to take one a day on Days 3, 4, and 5 of the Randomized Treatment period for the abdominal X-ray on Day 6.

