³Subjects are reminded during the Day 7 call of the Run-In period and Day 2 call of the Randomized Treatment period to begin taking the Sitzmark capsules the following day to prepare for the abdominal X-ray on Day 11 of the Run-In period and Day 6 of the Randomized Treatment period.

⁴Patients will wear an I-Button continuously from Day 8 of the Run-In period to Day 5 of the Wash-Out period except during periods of bathing.

⁵PK samples are taken pre-dose and 1, 2, 4, and 8 hours post-dose. A sample for liver function tests will be taken with the 8-hour post-dose PK draw.

⁶Visit 3 occurs on the day before randomization in non-PK subject

Table 4: Schedule of Events of Stage 2 under Protocol Dated 02 February 2018

Scheduled Assessments	Period 3.1 Run In					Period 3.2 Dose Escalation		Period 4 Fixed Dose		Period 5 Wash Out		
	Day 1 Visit 1 Screening	Days 2-7, 9,10,12,13 Phone Calls	Day 8 Phone Call	Day 11 Visit 2	Day 14 Phone Call	Days 1-13 Phone Calls	Day 14 Phone Call	Days 1-3 Phone Calls	Day 4 Visit 3	Days 1-7 Phone Calls	Day 14 Visit 4	Day 28 FU Call
Informed Consent	X											
Inclusion/Exclusion Criteria	X											
Demographics/Medical History	X											
Concomitant Medications	X	X	X	X	X	X	X	X	X	X	X	
Complete Physical Exam	X											X
Height	X											
Weight	X			X					X		X	
Vital Signs (1)	X			X					X		X	
EKG	X								X		X	
Local Labs: Chemistry*, Hematology*	X								X		X	
Local Labs: Coagulation Panel*	X											
Local Labs: Serum Pregnancy (2a) or FSH (2b)	X											
Urinalysis* (dipstick)	X								X		X	
Urine Pregnancy Test (3)				X					X		X	
Fecal Occult Blood (4)	X								X		X	
Study Drug Dispense, Accountability, Collection				X					X			
Reminder to Begin Taking Study Drug the Next					X							
Instruction to Discontinue Laxatives and Other Restricted Medications (5)	X											
Instruction to Resume Laxatives and Other Restricted Medications										X (6)		
Stool and Sleep Diary Instruction/Review	X	X	X	X	X	X	X	X	X	X	X	
AE Assessment and Review	X	X	X	X	X	X	X	X	X	X	X	X
Rome IV Questionnaire	X		X									
UPDRS	X								X		X	
PAC-QOL and PAC-SYM	X				X		X		X		X	
BDI-II, NMSQ, PFS-16, UM-PDHQ, MMSE, Trail-Making A and B, RBDQ, PDSS	X								X		X	
I-Button	X (7)		X						X (9)	X (10)		

* Refer to Appendix 1 for full list of clinical laboratory assessments

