- (1) The first blood pressure and heart rate will be taken after the subject has been in the supine position for at least 5 minutes. The second blood pressure and heart rate reading will be taken while the subject is standing, within 5 minutes of standing from the supine position. All other vital signs (respiration rate and body temperature) will be taken after the subject has been sitting or standing for 5 minutes.
- (2) (2a) For women of child-bearing potential and (2b) For post-menopausal women less than 60 years of age.
- (3) For women of child-bearing potential, done on site with urine pregnancy kit provided
- (4) Subjects will be provided a home testing kit with instructions; to be used at home on the first bowel movement following the visit, and results to be given to the study coordinator at subsequent phone call visit.
- (5) Subjects will be instructed to discontinue all laxatives, bulking agents, softeners and suppositories as well as clonazepam, opiates, etc. as specified in the protocol. Proton pump inhibitors and antacids may be continued until the end of the Run-In Period.
- (6) Subjects will be instructed to resume use of their regular regimen laxatives, bulking agents, softeners, proton pump inhibitors, and antacids after week 1 of wash out.
- (7) Dispense I-Button
- (8) Instruct subjects to begin wearing the I-Button
- (9) Instruct subjects to stop wearing the I-Button at the end of Day 5 of Wash Out
- (10) Collect I Button

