7.7 Analysis of Pharmacodynamics Data

Generally speaking, for Stage 1 and Stage 2, the summaries will be provided for active treatment ENT-01 or by dose level if deemed as necessary. The comparison is made to baseline for each PD variable up to the end of fixed dosing period plus washout period.

For Randomized population of Stage 2, the descriptive summaries will be provided for active treatment and placebo. Due to small sample size resulting from amended protocol, there will be no formal statistical comparisons between active treatment and placebo for PD variables.

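### Stage 2 washout stool-diary summaries pool a rescue-only week with a week on resumed laxatives, so their comparison with baseline mixes two bowel regimens

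*SAP*

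**What the plan says.** **Regimen.** Protocol Section 3.1, Period 5, takes patients off study drug for two weeks. For week 1 it says: "During the first week of the wash-out period they will only use rescue medication as needed". For week 2: "During the second week, they will be restarted on all original medications including laxatives". The February 2018 schedule (SAP Table 4, footnote 6) has patients "resume use of their regular regimen laxatives, bulking agents, softeners, proton pump inhibitors, and antacids after week 1 of wash out". In the run-in (Protocol Section 3.1, Period 3.1), laxatives, bulking agents and softeners are stopped and rescue is allowed.

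**Analysis.** SAP Section 4.4 starts the Stage 2 washout 24 hours after the last dose and makes no split at day 7. SAP Section 9 describes the parameters as "all evaluated using two weeks of washout data, i.e., the end of 2 weeks". SAP Section 7.7 adds: "The comparison is made to baseline for each PD variable up to the end of fixed dosing period plus washout period". SAP Section 7.7.2 lists washout among the periods for categorical parameters, which include Success; the one Success estimate it specifies is at the end of the fixed period.

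**Counting.** SAP Section 4.4.1 does not count stools within 24 hours of rescue. It divides CSBM and SBM by all diary days and multiplies by 7. Its rescue-use measure names laxatives, suppositories and enemas, but not softeners or bulking agents.

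**Deleted analysis.** SAP Sections 1 and 9 drop the comparison of Success at the end of washout week 1 because that window differs from the two weeks used for other parameters.

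**The concern.** A washout summary set against baseline is normally read as showing whether patients return to their pre-drug state once the drug stops. That reading needs a background treatment similar to baseline. Here it changes halfway through the window, and the SAP does not mention the change. A pooled value near baseline, above it or below it could each owe something to the laxatives resumed in week 2.

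This matters somewhat more because the February 2018 amendment removed the randomised period and the SAP makes no formal comparison with placebo. What happens after ENT-01 stops is then one of the few remaining supports for attributing the on-treatment change to the drug. The SAP has also deleted the one planned washout Success analysis confined to week 1.

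**Working it through.** The plan states no washout figure to reproduce. The check sets the rules side by side and then works through the SAP formulas. All rates below are assumptions, because the documents give none for washout.

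**1. Background by window (Stage 2).**

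| Window | ENT-01 | Regular laxatives, softeners, bulking agents |
|---|---|---|
| Run-in | none | stopped; rescue allowed |
| Washout Days 1–7 | none | rescue only |
| Washout Days 8–14 | none | resumed (Period 5 text; SAP Table 4) |

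**2. Day-based rates.** The SAP rate is qualifying days ÷ diary days × 7. With 7 + 7 complete diaries the pooled rate is the plain average (r1 + r2)/2 of the two weekly rates, so half the weight comes from the second regimen. Missing diaries are not imputed (SAP Section 8.3), so the weight can differ between patients.

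**3. Direction.** Let k be the number of week-2 days blocked by the 24-hour rule, and w the counted rate on unblocked week-2 days divided by the week-1 rate. Then pooled ÷ week-1 rate = [7 + (7 − k)w]/14.

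| k | w = 1 | w = 1.25 |
|---|---|---|
| 0 | 0% | +12.5% |
| 1 | −7.1% | +3.6% |
| 2 | −14.3% | −5.4% |
| 4 | −28.6% | −23.2% |
| 7 | −50.0% | −50.0% |

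The two effects cancel at w = 7/(7 − k): 1.17, 1.40 and 2.33 for k = 1, 2 and 4. A value of w above 1 could arise from laxative effect lasting beyond 24 hours. It could also arise from stools aided by softeners or bulking agents that are not captured as rescue.

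**4. Success.** The rule is a rise of at least 1 CSBM day/week over baseline, or 3 or more per week. Take a baseline of 1.
- Week 1 = 1, week 2 = 3 to 5: pooled (1 + 3)/2 = 2.0 to (1 + 5)/2 = 3.0, a success. Week 1 alone is not.
- Week 1 = 3, week 2 = 0 because every stool is filtered: pooled (3 + 0)/2 = 1.5, not a success. Week 1 alone is.

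**5. Rescue use.** With 1 day in week 1 and regular laxatives recorded as rescue on 3 to 7 days of week 2, the pooled value is (1 + 3)/2 = 2.0 to (1 + 7)/2 = 4.0 days/week, against 1.0 in week 1.

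**6. Ease and consistency.** These divide by counted stools, not days, so blocked days do not dilute them. Week-2 stools that pass the filter still enter the average, with weight equal to their share of all counted stools. They mix regimens too.

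**7. Is a common window length needed?** Every frequency formula rescales to 7 days. Protocol Section 3.1, Period 3.2, calculates the fixed-dose rate over the fixed-dose days alone, 2 to 4 of them, while the run-in lasts two weeks. The main comparison therefore already uses unequal windows.

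**8. Timing of resumption.** Under the July 2017 protocol, the Period 5 text places it in week 2. The Appendix 2 row "Instructions to Resume Laxatives and other BM medications" is marked at washout Day 14, and SAP Table 3 words that Day 14 row "Instructions to Discontinue Laxatives and other BM medications". In the February 2018 table the row "Instruction to Resume Laxatives and Other Restricted Medications" is marked under washout Days 1–7, which fits its footnote. The conflict is thus within the July 2017 material. Patients who resumed only at Day 14 would have k near 0 and little or no mixing.

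**The case against.** The strongest reply is that little rests on these summaries. They are descriptive, the primary test does not touch them, and washout Success follows only from a general lead-in. Rescue use by period, the diary listings and the medication listings would let a careful reader separate the weeks. All of that stands, and it is why the point is minor. It does not make the pooled change from baseline interpretable as tabulated.

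Two weeks also has some rationale: it equals the run-in length, and PAC-SYM and PAC-QOL have two-week recall. But equal length does not give equal background treatment. Those questionnaires, completed at washout Day 14, look back over both regimens and cannot be split.

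A reader might infer several stronger things that the documents do not support:

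- *That the pooled window is not off-drug.* Patients are off ENT-01 in both weeks; only the bowel regimen changes.
- *That week 1 reproduces baseline exactly.* It is closer, not identical. SAP Table 4, footnote 5, lets proton pump inhibitors and antacids continue to the end of run-in, while footnote 6 resumes them only after washout week 1. The July 2017 protocol also asks patients to avoid suppositories and enemas around the run-in Sitzmarks test.
- *That the 24-hour rule is itself at fault.* Excluding those stools follows the endpoint definition and applies in run-in as well.
- *That pooling biases in a known direction.* Steps 3 and 4 show that either sign is possible.

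**Conclusion.** The concern holds for Stage 2 washout CSBM, SBM, ease, consistency and rescue use, and for Success if it is summarised for washout. The pooled window mixes withdrawal of ENT-01 with the restart of laxatives, so its change from baseline cannot be assigned to either. The percentages in the working are illustrations: they assume complete diaries and invented values of k and w. The documents establish the mixing, not its size or sign, and the July 2017 timing conflict means that some patients may have had little of it.

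Consistency with the two-week window is not a sound reason for dropping the week-1 Success comparison, since the formulas rescale each window and week 1 is the part closer to the run-in background. Severity is minor: descriptive outputs only, with the primary test against 0.10 and the fixed-dose versus run-in comparison untouched.

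**What to change.** - Summarise Stage 2 washout stool-diary parameters separately for Days 1–7 (off ENT-01, rescue only) and Days 8–14 (off ENT-01, laxatives resumed). Use recorded resumption dates where available and give the diary-day count in each window.
- Use Days 1–7 for the comparison with baseline.
- State whether softeners and bulking agents count as rescue in the SAP formulas.
- Restore the comparison of Success at washout week 1 with the end of the fixed-dose period, as SAP Section 9 words it, as a descriptive summary for patients whose last dosing before washout was ENT-01. Note that this is not the randomised ENT-01 group of Protocol Section 10.5.
- Footnote that washout PAC-SYM and PAC-QOL recall spans both regimens.
- Reconcile the July 2017 passages on resumption: the Period 5 text, the Day 14 row in Appendix 2, and the wording of that row in SAP Table 3.

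The cost is SAP wording and programming; the diaries are already daily. The one loss is resolution: with 7 diaries one CSBM day moves a patient's rate by 7/7 = 1 per week, against 7/14 = 0.5 with 14.
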